5.0 CRITERIA FOR SUBJECT ELIGIBILITY

5.1 Subject Inclusion Criteria

In order to be eligible to participate in this study, a subject must meet all of the following criteria:

- Healthy volunteers, 18 to 45 years of age, inclusive. Healthy status is defined by absence of evidence of any active or chronic disease following a detailed medical and surgical history.
- Body mass index (BMI) between 18 and 30 kg/m², inclusive, and with a minimum weight of 50 kg.
- Able to participate and willing to give written informed consent and to comply with the study restrictions.

5.2 Subject Exclusion Criteria

A potential subject who meets any of the following criteria will be excluded from participation in this study:

- History or symptoms of any significant disease including (but not limited to), neurological, psychiatric, endocrine, cardiovascular, respiratory, gastrointestinal, hepatic, or renal disorder.
- Systolic blood pressure (SBP) greater than 140 or less than 90 mm Hg, and diastolic blood pressure (DBP) greater than 90 or less than 50 mm Hg.
- Use of any medications (prescription or over-the-counter [OTC]), vitamin, mineral, herbal, and dietary supplements within 21 days of study drug administration, or less than 5 half-lives (whichever is longer). Exceptions are paracetamol (up to 4 g/day). Other exceptions will only be made if the rationale is discussed and clearly documented between the Investigator and the sponsor.
- Concomitant disease or condition that could interfere with, or for which the treatment of might interfere with, the conduct of the study, or that would, in the opinion of the Investigator, pose an unacceptable risk to the subject in this study.
- Smokers as defined by any of the following criteria:
 - Reported smoking of cigarettes within 12 months prior to screening; occasionally a cigarette is allowed, but not within 24 hours of the measurements.
- Any confirmed significant allergic reactions (urticaria or anaphylaxis) against any drug, or multiple drug allergies (non-active hay fever is acceptable).

- Unwillingness or inability to comply with the study protocol for any other reason.

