4.0 OVERVIEW OF STUDY DESIGN/INTERVENTION

4.1 Design

This study is a non-therapeutic open observational trial, which evaluates the feasibility of the hyperspectral camera system (a non-significant risk device) in evaluation of the tissue perfusion and oxygenation in different circumstances. The exploratory aim of this study is to select relevant spectral bands for oxygenation and perfusion detection, which can be used for further camera development and consequently in clinical practice. Eight healthy volunteers, without any medication use and without any relevant medical history will be included in this study. Subjects will be enrolled following confirmation of study eligibility (section 5.0) which will be checked at baseline. Reproducibility will be validated by performing the following HCS measures:

- Basal blood flow
- Blood flow upon occlusion-reperfusion brachial artery
- Blood flow after applying capsaicin-based cream
- The room temperature, which could influence the skin perfusion will also be measured.

For the secondary endpoints, hyperspectral measures of:

- basal blood flow / oximetry
- blood flow /oximetry upon occlusion-reperfusion brachial artery
- Blood flow / oximetry after applying capsaicin-based cream

Reproducibility will be validated by the HCS measure only, at both time points that the HCS is used.

Explorative endpoint:

The explorative endpoint of the study is to see if a selection of spectral bands, specific for tissue perfusion and oxygenation (selected after data processing of above mentioned measurements) can be achieved.

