7.0 ASSESSMENT/EVALUATION PLAN

Subjects will participate on 2 similar study days, separated by a minimum of 3 days and maximal 28 days. Measurements will be assessed by the HCS and will take maximum 2 hours.

Pre-treatment evaluation (after study consent and registration of volunteers):

- Medical history review
- Weight

Once eligibility is confirmed:

- Blood pressure
- Heart rate
- Room temperature

On study procedures to be followed:

- 1) The volunteer is installed at the test location (Pre-surgical Center, M-6) at the main hospital

- 2) Before starting the measurements, the blood pressure, heart rate and room temperature are measured to establish the baseline characteristics.
- 3) The volunteer is asked to stretch both forearms near to each other in sitting position.
- 4) The blood flow is measured by the HCS at baseline on both forearms (Total field of view: max. 10 x 10 cm)
- 5) After baseline measurements the flow is measured on either the right or left forearm during five minutes occlusion (a blood pressure cuff will be used) of the right brachial artery and during five minutes of reperfusion after occlusion.
- 6) After taking these measurements, there is a short break of 5 minutes, to save all measurements.
- 7) Local capsaicin-based cream is administrated on the same forearm on an area of 3 x 3 cm, on a distance of 5 cm under the radiocarpal joint.
- 8) 30 minutes after application of the crème, crème is removed from the skin.
- 9) For obtaining optimal flare, 20 minutes after removing the crème, the perfusion is measured by HCS for 5 minutes.
- 10) Region with administrated local capsaicin-based cream is compared to control regions located on the same forearm,
- 11) After 10 minutes the procedure is finished.

Concomitant medications and alcohol/caffeine consumption

The use of the following concomitant medications is prohibited: no prescription medications, over-the-counter (OTC) medications, vitamin, herbal and dietary supplements will be permitted within 14 days prior to study drug administrations, or less than 5 half-lives (whichever is longer, and during the course of the study. The following exceptions are applied:

- paracetamol (up to 4 g/day).
- Other exceptions will only be made if the rationale is discussed and clearly documented by the investigator

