10.0 CRITERIA FOR REMOVAL FROM STUDY

Participants may withdraw from the study at any time. If at any time the participant is deemed ineligible for the study, they will be removed from the study.

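### Section 5.2 joins the systolic and diastolic limits with 'and', so read literally a volunteer with only one pressure out of range is not excluded by that criterion

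*Combined protocol and SAP*

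**What the plan says.** Section 5.2 opens with the rule for combining its criteria: "A potential subject who meets any of the following criteria will be excluded from participation in this study". One bullet then sets the pressure limits, with systolic pressure "greater than 140 or less than 90 mm Hg, and diastolic blood pressure (DBP) greater than 90 or less than 50 mm Hg". These are the only numerical blood-pressure limits in the document.

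Other text bears on the same volunteers:

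- **Section 5.1** requires healthy volunteers: "Healthy status is defined by absence of evidence of any active or chronic disease following a detailed medical and surgical history".
- **Section 5.2** has a further bullet that lets the investigator exclude a person whose disease or condition is judged an unacceptable risk. It has no pressure threshold.
- **Section 10.0** provides for removal: "If at any time the participant is deemed ineligible for the study, they will be removed from the study".

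On timing, Section 4.1 states: "Subjects will be enrolled following confirmation of study eligibility (section 5.0) which will be checked at baseline". Section 7.0 lists blood pressure under the heading "Once eligibility is confirmed", and its step 2 reads: "Before starting the measurements, the blood pressure, heart rate and room temperature are measured to establish the baseline characteristics". The schedule in Section 9.0 marks blood pressure at Visit 1 and not at Screening. Section 12.1 has an Eligibility Checklist completed during registration, and its signer confirms whether the participant is eligible. The checklist itself is not among the documents.

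**The concern.** The bullet uses 'or' between the upper and lower limit of each pressure, and 'and' between the two pressures. Taken at its word, it excludes only a person who is out of range on both. An isolated high systolic or an isolated high diastolic reading would pass, which is hardly what a study of healthy volunteers intends.

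The rule matters because it is the only numerical cardiovascular limit on entry. Section 14.0 relies on careful selection of volunteers, together with a controlled hospital setting, to keep drug risk low. Section 8.0 counts hypertension among the gravest reactions reported for capsaicin cream. Two careful readers of the bullet could also reach opposite decisions on the same volunteer, and an eligibility rule should not allow that.

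**Working it through.** The plan gives no figure to reproduce, so the check is a matter of logic.

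**Inputs (Section 5.2).** Let S mean systolic pressure (SBP) >140 or <90 mm Hg, and D mean diastolic pressure (DBP) >90 or <50 mm Hg. Meeting any one bullet excludes.

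**Rule as written:** S and D. **Evident intent:** S or D. The any-of-these rule works across bullets. It does not change the 'and' inside this one.

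**Counting patterns.** Each pressure can be low, in range or high, which gives 3 × 3 = 9 combinations. Low systolic with high diastolic is impossible, because diastolic lies below systolic, so 8 remain. Removing the pattern with both in range leaves 7 with at least one pressure out of range.

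| Systolic | Diastolic | Example | As written | With 'or' |
|---|---|---|---|---|
| high | high | 150/95 | excluded | excluded |
| low | low | 85/45 | excluded | excluded |
| high | low | 150/45 | excluded | excluded |
| high | in range | 170/85 | not excluded | excluded |
| in range | high | 120/105 | not excluded | excluded |
| low | in range | 85/60 | not excluded | excluded |
| in range | low | 100/45 | not excluded | excluded |

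The bullet as written excludes 3 of 7; with 'or' it excludes 7 of 7. This counts patterns, not people, because the documents give no blood-pressure distribution.

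**Could another rule fill the gap?** The healthy-status rule in Section 5.1 rests on history. It covers known hypertension, but not reliably an isolated abnormal reading in someone with no such history. The investigator-opinion bullet can exclude a person seen at 170/85, but by judgement. Section 10.0 applies to a person already deemed ineligible, so it depends on the pressure bullet or on that same judgement.

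**Timing.** Section 5.2 needs a pressure value to decide eligibility. Section 7.0 places the reading after eligibility is confirmed, and Section 9.0 schedules none at Screening. Sections 7.0 and 9.0 describe the Visit 1 reading as a baseline characteristic and do not say that it decides eligibility, although Section 4.1 says eligibility is checked at baseline.

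**Cost in screen failures.** Let p be the share of otherwise eligible volunteers with exactly one pressure out of range. The documents do not give p; 1% to 10% is assumed. The extra failures expected in enrolling 8 are 8/(1 − p) − 8 = 8p/(1 − p):

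- p = 0.01: 0.08/0.99 = 0.08
- p = 0.05: 0.40/0.95 = 0.42
- p = 0.10: 0.80/0.90 = 0.89

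**The case against.** The strongest reply is that everyone knows what is meant. Staff would very likely treat either value as excluding, 'and' can be read as merely listing two limits, and nothing in the documents shows anyone applying the literal reading. There is also a real backstop: an investigator who sees an abnormal reading at step 2 can exclude under the investigator-opinion bullet, and Section 10.0 then requires removal. This stands as mitigation and keeps the point minor. It does not repair the rule, because neither provision contains a number, and the wording of the unseen checklist cannot be assumed to be right.

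Three stronger readings are tempting, and the documents support none of them.

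- **The error puts volunteers at measurable extra risk.** Section 8.0 gives a rate of 0.01–0.1% for the gravest capsaicin reactions, and a reader might turn that into harm avoided. Nothing says that an isolated out-of-range pressure raises this rate. If the same rate applies to the people who replace those excluded, the expected number among eight is 8 × rate before and after the correction. Two of the four missed patterns are low pressures, to which a concern about hypertension does not apply.
- **Volunteers undergo occlusion or receive cream before any pressure is known.** Step 2 of Section 7.0 takes a reading before the measurements start, ahead of both.
- **Section 7.0 contradicts Section 12.1.** Both place registration early, and taking pressure after eligibility is confirmed fits a checklist completed at registration. The true tension is narrower: Section 5.2 needs a value that the schedule does not supply by then.

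**Conclusion.** The point holds as a wrong-as-written eligibility rule. The blood-pressure bullet misses 4 of the 7 possible out-of-range patterns, and no other provision replaces its number. This rests on the ordinary meaning of 'and', on the any-of-these rule working across bullets only, and on diastolic pressure lying below systolic.

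The size is small. The intent is evident, discretionary safeguards exist, and neither the t-tests nor the coefficient of variation in Section 11.0 uses blood pressure, so no endpoint or analysis changes. No reduction in harm can be claimed. The correction is worth making because it concerns an operative safety threshold and costs almost nothing. The unclear timing of the reading is a secondary matter.

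**What to change.** In Section 5.2, replace the 'and' between the two pressures with 'or', or split the bullet into two exclusion lines with the cut-offs unchanged:

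- SBP >140 or <90 mm Hg
- DBP >90 or <50 mm Hg

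Use the same wording on the Eligibility Checklist.

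Optionally, add a cuff reading at Screening, after consent and before the checklist is signed, and keep the Visit 1 reading as the baseline value. The signer then has a pressure to certify. Merely declaring the Visit 1 reading decisive would not achieve this, because the checklist is completed at registration.

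The cost is a wording change in one bullet and on the checklist, plus one cuff reading per volunteer and a matching entry in Sections 7.0 and 9.0 if the option is taken. Recruitment may lose a volunteer or two: 0.08 to 0.89 extra screen failures are expected under the assumed 1% to 10%, and none if staff already exclude on either value.

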6.0 RECRUITMENT PLAN

Enrollment in this study will be open to all MSK employees to act as healthy volunteers provided they meet eligibility criteria. Every effort will be made to include women and minorities in the research study. Employees who provide consent willfully and voluntarily may participate as a healthy volunteer once. The volunteers will primarily be recruited from members of the Department of Radiology who are willing to participate via word of mouth. To prevent departmental researchers from feeling pressured into participating in this study (i.e., where there is a status relationship), it is a Department policy to strictly forbid a person to ask a subordinate employee to participate in an evaluation. This policy is described to each new researcher as part of their research training, and all members are routinely reminded of this study policy during research meetings. Participation will occur outside of the employee's usual working hours.

Participants will be offered a \$50 dollar gift card for their participation.

During the initial conversation between the investigator/research staff and the participant, the participant may be asked to provide certain health information that is necessary to the recruitment and enrollment process. If the participant turns out to be ineligible for the research study, the research staff will destroy all information collected on the participant during the initial conversation and medical records review. ..

..

7.0 ASSESSMENT/EVALUATION PLAN

Subjects will participate on 2 similar study days, separated by a minimum of 3 days and maximal 28 days. Measurements will be assessed by the HCS and will take maximum 2 hours.

Pre-treatment evaluation (after study consent and registration of volunteers):

- Medical history review
- Weight

Once eligibility is confirmed:

- Blood pressure
- Heart rate
- Room temperature

On study procedures to be followed:

- 1) The volunteer is installed at the test location (Pre-surgical Center, M-6) at the main hospital

- 2) Before starting the measurements, the blood pressure, heart rate and room temperature are measured to establish the baseline characteristics.
- 3) The volunteer is asked to stretch both forearms near to each other in sitting position.
- 4) The blood flow is measured by the HCS at baseline on both forearms (Total field of view: max. 10 x 10 cm)
- 5) After baseline measurements the flow is measured on either the right or left forearm during five minutes occlusion (a blood pressure cuff will be used) of the right brachial artery and during five minutes of reperfusion after occlusion.
- 6) After taking these measurements, there is a short break of 5 minutes, to save all measurements.
- 7) Local capsaicin-based cream is administrated on the same forearm on an area of 3 x 3 cm, on a distance of 5 cm under the radiocarpal joint.
- 8) 30 minutes after application of the crème, crème is removed from the skin.
- 9) For obtaining optimal flare, 20 minutes after removing the crème, the perfusion is measured by HCS for 5 minutes.
- 10) Region with administrated local capsaicin-based cream is compared to control regions located on the same forearm,
- 11) After 10 minutes the procedure is finished.

Concomitant medications and alcohol/caffeine consumption

The use of the following concomitant medications is prohibited: no prescription medications, over-the-counter (OTC) medications, vitamin, herbal and dietary supplements will be permitted within 14 days prior to study drug administrations, or less than 5 half-lives (whichever is longer, and during the course of the study. The following exceptions are applied:

- paracetamol (up to 4 g/day).
- Other exceptions will only be made if the rationale is discussed and clearly documented by the investigator

Both alcohol and caffeine consumption could influence the skin perfusion [14, 15]. Therefore, alcohol and caffeine consumption is prohibited within 12 hours preceding both study days. Before starting the measurements, the blood pressure, heart rate and room temperature will be measured to establish the baseline characteristics.

8.0 TOXICITIES/SIDE EFFECTS

HCS: No side effects were expected, because imaging of the skin perfusion is a non-invasive procedure. This technique only uses halogen light as light source, which is also widely used in commercially available light sources.

Capsaicin cream (FDA approved): The concentration used for this study is 0.075%, which is commonly used in clinical practice. Some side effects were reported by using capsaicin-based cream. In 0.01-0.1% hypertension, first-degree AV block and tachycardia were reported, which were the most dangerous complications. Other complications, such as local skin irritation, local pain and erythema are more commonly seen. No interactions with other drugs were reported.

9.0 PRIMARY OUTCOMES

Assessment	Screening	Visit 1	Visit 2 (to occur between 3 and 28 days after Visit 1)
Medical History	X		
Weight	X		
Blood pressure		X ¹	
Heart Rate		X ¹	
Room temperature		X ¹	
HCS measurements		X ²	X
Creme applications		X	X

¹Before starting HCS measurements, blood pressure, heart rate and room temperature will be measured to establish baseline characteristics.

²Blood flow is measured by HCS and on both forearms at baseline (Total field of view: max. 10 x 10 cm). After baseline measurements the flow is measured on either the right or left forearm during five minutes occlusion of the right brachial artery and during five minutes of reperfusion after occlusion. After taking these measurements, there is a short break of 5 minutes, to save all measurements.

The detailed study procedures to be followed are outlined in section 7.0.

10.0 CRITERIA FOR REMOVAL FROM STUDY

Participants may withdraw from the study at any time. If at any time the participant is deemed ineligible for the study, they will be removed from the study.

11.0 BIOSTATISTICS

Primary study parameter(s)

Reproducibility is measured by performing the measurements on two different days in the same study population. Sample T-tests will be used for comparison of the perfusion

measured by the HCS system and room temperature in the eight recruited human volunteers. The intra-subject variability over the two measurement moments will be established by calculation of the coefficient of variation.

Secondary study parameter(s)

For spectral measurements no specific statistical analysis is performed. It is mainly a part of data processing as described in the study design protocol section 4.0.

Leiden University Medical Center (LUMC) is utilizing their own protocol under their own regulatory body oversight, and conducting separate but similar protocols. LUMC data will be pooled with our data for analysis.

The PI of this study will be sharing de-identified data with an external collaborator at Leiden University Medical Center for the purpose of data analyses. Anonymized images taken from the hyperspectral camera will be electronically sent to Quest Medical Imaging for analysis.

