1.0 PROTOCOL SUMMARY AND/OR SCHEMA

This is an open observational study being done to test the feasibility and reproducibility of a hyperspectral camera system (HCS) in human skin perfusion. Oxygenation detection will be evaluated, resulting in selection of spectral bands, which could be used in clinical practice. Eight healthy volunteers will be included.

Feasibility and reproducibility of a hyperspectral camera system in human skin perfusion and oxygenation detection will be evaluated, resulting in selection of spectral bands, which could be used in clinical practice.

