2.0 OBJECTIVES AND SCIENTIFIC AIMS

Primary Objective:

To investigate the feasibility, applicability, and reproducibility of a novel hyperspectral camera system in perfusion and oxygenation detection in healthy volunteers.

Secondary Objectives:

- To explore the effect of occlusion-reperfusion of the brachial artery on cutaneous blood flow as assessed by a hyperspectral camera system.
- To explore the effect of applying topical vasoconstrictors / vasodilators on the cutaneous blood flow as assessed by a hyperspectral camera system.
- Selection of relevant spectral bands for oxygenation and perfusion detection.

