4.2 Intervention

The capability of the HCS in detection of tissue perfusion and oxygenation in eight human volunteers during different circumstances: before/after occlusion brachial artery, before/after application capsaicin-based cream..

Quest Hyperspectral imaging system

The HCS is not approved by the US Food and Drug Administration. The device qualifies as non-significant risk because it is not used as an implant, nor is it used to sustain human life, nor will it be used in diagnosing, curing, mitigating or treating disease and does not present a potential for serious risk to the health, safety, or welfare of a subject.

The device is designed for medical applications and has optimized optics for spectral analysis of biological compounds. In this camera 3 sensors are combined for optimal spectral imaging. For 2D reference, and to facilitate annotating the data, a high resolution (full HD) color image, recorded with an RGB-sensor, is included with each hyperspectral dataset. The spectral bands are acquired using a 4x4 mosaic sensor for the spectral range of 470 – 630 nm, this sensor is referred to as the VIS-sensor. The NIR-sensor is a 5x5 mosaic sensor with a spectral range of 600 – 950 nm (see Figure 1 for an impression of the transmission bands of the sensor pixels). The color image is co-registered with the hyperspectral data with subpixel accuracy, making accurate data fusion and visualization methods possible.

This hyperspectral camera is based on a tiled-filter approach where pixels are individually filtered with narrow Fabry-Pérot bandpass filters. This method allows real-time imaging at video frame rates without the need to scan in either the spatial dimension (e.g. moving the camera) or the spectral dimension (e.g. changing the pass-through characteristics of an optical filter).

The Quest hyperspectral imaging system has 41 spectral bands, equally distributed in the visible-near infrared (VIS-NIR) range of the electromagnetic spectrum (450 – 950 nm). The time it takes to capture the hyperspectral images and obtaining feedback from the instrumentation is around 2-3 seconds, which is nearly real time. The field of view is 10 x 10 centimeter, which makes this camera system suitable for clinical use in the future. It delivers images with a 10 frames per second framerate.

[figure not shown]
The device has been supplied to MSK by Quest Innovations.

Data analysis HCS

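### The two-day coefficient of variation mixes camera error with day-to-day change in skin perfusion, so a high value could not be attributed; a repositioned repeat baseline image in each session would make the split estimable

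*Combined protocol and SAP*

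**What the plan says.** The primary objective in Section 2.0 is "To investigate the feasibility, applicability, and reproducibility of a novel hyperspectral camera system in perfusion and oxygenation detection in healthy volunteers". Section 1.0 gives the size: "Eight healthy volunteers will be included".

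Section 11.0 defines the replication: "Reproducibility is measured by performing the measurements on two different days in the same study population". The results are summarised by t-tests and by an intra-subject CV over the two occasions. Section 4.1 likewise confines reproducibility to the two time points, and Section 7.0 separates them by 3 to 28 days.

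In each session, step 4 of Section 7.0 is a single baseline step: "The blood flow is measured by the HCS at baseline on both forearms". Occlusion, reperfusion and, later, post-cream recordings follow, each of five minutes. No repeat acquisition, repositioning, phantom measurement or variance-component analysis is planned.

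The protocol accepts that perfusion itself moves. Section 4.1 says "The room temperature, which could influence the skin perfusion will also be measured", and Section 7.0 says "Both alcohol and caffeine consumption could influence the skin perfusion". It prohibits alcohol and caffeine for 12 hours before both study days. Section 7.0 has blood pressure, heart rate and room temperature taken before the measurements, but the table in Section 9.0 marks them at Visit 1 only.

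**The concern.** The objective concerns a property of the device, but the planned replication changes the device set-up and the state of the skin together. If each volunteer contributes one summary value per condition per day, the within-subject variance across days has at least two sources: camera and positioning error, and true change in perfusion over 3 to 28 days. The plan estimates only their sum.

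The ambiguity is one-sided. If the true two-day variability is low, both parts must be low, and the result supports the camera. If it is high, the plan cannot say whether the instrument is noisy or the skin varied. For a first study in humans of a prototype, those two readings call for different next steps.

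**Working it through.** **Inputs from the documents.** 8 volunteers (Section 1.0); 2 days each, 3 to 28 days apart (Section 7.0); capture time of 2 to 3 seconds (Section 4.2); session limit of 2 hours (Section 7.0).

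**Not given.** Camera SD, day-to-day SD, acceptable CV, alpha and power. The sample size therefore has no stated derivation to reproduce, and every SD or CV below is an assumption for illustration.

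**1. Only the sum is estimable.** Model: reading = subject + day + camera error. With one value per day, two-day variance = day variance + camera variance.

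- Camera CV 5%, physiology CV 20%: √(25 + 400) = 20.6%; camera share 25/425 = 6%.
- Camera CV 20%, physiology CV 5%: √(400 + 25) = 20.6%; camera share 400/425 = 94%.

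**2. The planned statistics do not respond to the split.** A total within-subject SD of 15 on a mean of 100 was divided three ways, with 40,000 simulated trials of 8 subjects per split. The t-test is read as a paired two-sided 5% comparison of days. The last two columns are median estimates (95% range) with two exchangeable readings per session.

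| True camera / day SD | Planned two-day SD, median | Planned t-test rejects | Camera SD, two readings | Day SD, two readings |
|---|---|---|---|---|
| 5 / 14.1 | 14.3 | 5.1% | 4.9 (3.3–6.7) | 13.5 (6.7–21.3) |
| 10.6 / 10.6 | 14.4 | 5.0% | 10.4 (7.0–14.3) | 10.0 (0–17.8) |
| 14.1 / 5 | 14.3 | 4.9% | 13.8 (9.3–18.9) | 4.3 (0–13.5) |

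The planned columns are the same in all three rows. The t-test looks only for a mean shift between days (80% power at 1.16 SD of the differences with n = 8) and carries no information on the split.

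**3. Precision.** 95% limits for an SD are √(df/χ²₀.₉₇₅) to √(df/χ²₀.₀₂₅) times the estimate.

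- Two-day SD, 8 df if no mean shift is assumed: 0.68 to 1.92. With the shift removed, 7 df: 0.66 to 2.04.
- Same-session SD from one pair per session, 8 × 2 = 16 df: 0.75 to 1.52 (0.745 to 1.522 before rounding).

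With two readings per session, day variance = (between-day mean square − within-session mean square)/2. In the third row this estimate was negative in 39% of simulated trials. The split becomes estimable, but the day component does not become precise.

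**4. Room in the session.** Steps 5 to 11 take 5 + 5 + 5 + 30 + 20 + 5 + 10 = 80 minutes. If the two-hour maximum applies to each session, 120 − 80 = 40 minutes remain for steps 1 to 4. One more capture is stated to take a time that "is around 2-3 seconds, which is nearly real time"; repositioning the arm is assumed to bring the addition to roughly a minute.

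**The case against.** **Test-retest across days is a legitimate definition of reproducibility, and this is an eight-person feasibility study.** True, and the two-day CV should stay. It answers how far a reading can be trusted from one day to another. It does not say how much of the variation belongs to the camera, which is what the objective names.

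**The plan controls physiology.** The 12-hour alcohol and caffeine ban applies before both days, and room temperature is named in the Section 11.0 comparison. These steps limit or describe part of the variation but do not estimate what remains. If the Section 9.0 table is followed, temperature is missing on the second day.

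**A reader might infer that a same-session repeat already exists in the images.** Untreated skin is imaged at step 4 and again after the cream, since "Region with administrated local capsaicin-based cream is compared to control regions located on the same forearm". The documents do not support using this as a repeatability estimate. They do not show that the later control regions lie within the step 4 field. The later image comes at least 5 + 5 + 5 + 30 + 20 = 65 minutes after occlusion begins, on the forearm that received the cream, and is timed for optimal flare. A systematic shift would load onto the within-session term. With camera CV 5%, physiology CV 20% and an assumed 20% shift, the within-session variance is 25 + 20²/2 = 225 and the between-day mean square is 2 × 400 + 25 = 825. The day component is then (825 − 225)/2 = 300, and the apparent camera share is 225/525 = 43% against a true 6%. Nor would the result be an upper bound on camera error, because calibration or illumination error that changes between days falls outside it.

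**The recordings hold many frames.** Five minutes at 10 frames per second is 5 × 60 × 10 = 3,000 frames. They share one set-up and include no repositioning, so at best they give a short-term noise floor. The occlusion and reperfusion recordings are also not steady state.

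**Data from the Leiden centre will be pooled.** This could add degrees of freedom. It would not separate the sources unless that protocol, listed as an appendix and not seen here, includes same-session repeats.

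**Conclusion.** The point holds and should be acted on. As planned, the primary reproducibility statistic estimates the sum of camera and positioning error and day-to-day physiology. The same 20.6% can conceal a camera share of 6% or 94%. Those CVs are assumed, since the documents give none, but the inability to separate the sources follows from the design whatever their size.

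A reader might infer that the trial could wrongly accept or reject the device. The documents do not support that. They contain no CV threshold or acceptance rule, and a truly low two-day total implies that both parts are low. Section 4.1 ties further camera development to the choice of spectral bands, not to the CV. What is lost is the interpretation of a high CV.

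**What to change.** **Section 7.0, step 4.** Acquire the baseline image twice in each session, with the arm repositioned in between and before any occlusion or cream.

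**Section 11.0.** Add, in substance: *Same-session repeatability (SD and CV) is estimated from the paired baseline images of each session. It is reported with 95% limits beside the between-day SD, as nested variance components with session within subject. The mean difference between first and second image is also reported.* The last item is there because the 16 df analysis treats the two images as exchangeable.

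State as a limitation that camera error changing between days, such as calibration or illumination, remains in the between-day term. That term should not be labelled pure physiology.

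**Cost.** Roughly a minute per session, with the same non-invasive camera and no new kind of procedure. The between-day component stays imprecise with 8 volunteers, and the text should say so. The repeat covers the baseline condition only; repeatability under occlusion or after the cream remains unseparated.
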